7.4 Adverse events: not structurally assessed

In addition to the safety outcomes that were structurally assessed, the study physician also asked the following questions at each study visit: Since your last study visit, did you experience any other new physical complaints or were you diagnosed with any other new conditions? Since your last study visit, have you taken any new medications? The answers given to those questions, and any other spontaneously reported adverse events, will be coded using MedDRA (version 19.0, March 2016) and will be reported in the same manner as described above for the structurally assessed adverse events.

8. Analyses of follow-up data: secondary efficacy outcomes

8.1 Incidence and incidence rate ratios of secondary efficacy outcomes

It has been hypothesised that a lactobacilli-dominated VMB would protect women from HIV, other STIs, and UTIs, and would facilitate pregnancy. While the sample size of this study was too small to adequately test these hypotheses, we did include incidence of HIV, STIs (other than TV), UTIs, and pregnancy as secondary outcomes. Women were tested for HIV and STIs (HSV-2, syphilis, CT, and NG) at the Screening and M6 visits, and for UTI and pregnancy at the Screening, Enrolment and M6 visits. In all cases, additional testing may have been done at the D7, M1 and M2 visits when clinically indicated. Incidence of these secondary outcomes will be determined between baseline (using endpoint data from the Enrolment visit if available and otherwise from the Screening visit) and M6.

Incident cases will be defined as follows:

- HIV: a positive result for the HIV serology algorithm at M6. Women who were HIV-positive at Screening were excluded from the study; therefore, all positive results at M6 will be treated as incident cases. Time at risk will start at the Enrolment visit.
- HSV-2: a positive result for HSV-2 serology at M6. Only those participants who tested negative for HSV-2 at Screening were retested at M6; therefore, all positive cases at M6 will be treated as incident cases. Time at risk will start at the Enrolment visit.
- Syphilis: a positive result for the syphilis serology algorithm at M6. All participants positive for syphilis at Screening were adequately treated prior to randomisation; therefore, all positive cases at M6 will be treated as incident cases. Time at risk will start at the Enrolment visit.
- NG: a positive result for NG PCR at M6 after a negative NG PCR result at Screening (time at risk will start at the Enrolment visit) or after having been successfully treated for NG during follow-up (time at risk will start on the treatment completion date).
- CT: a positive result for CT PCR at M6 after a negative CT PCR result at Screening (time at risk will start at the Enrolment visit) or after having been successfully treated for CT during follow-up (time at risk will start on the treatment completion date).
- UTI: a positive urinalysis result (according to the Rwandan guidelines) at M6 or earlier during follow-up if tested due to symptoms after a negative urinalysis dipstick result at an earlier visit or after adequate UTI treatment. Time at risk will always start at the Enrolment visit because all UTI's at the Screening and Enrolment visits were treated prior to randomisation.
- Pregnancy: a positive urine pregnancy test at M6 (or earlier during follow-up). As being pregnant at Screening or Enrolment was a reason for exclusion in this study, all positive results will be treated as incident cases.

Incidence rates: IRs will be calculated as the number of incident cases per person-days (PD) of follow-up with 95% confidence intervals using the IR function in STATA. IRs will be calculated for each primary endpoint in each of the 4 randomisation groups and for the entire study population. In all cases, IRs will be calculated for the entire follow-up period as described above.

	Group 1		Group 2		Group 3		Group 4		Total	
	n/N ¹	Cases/PD (IR, 95% CI) ²	n/N¹	Cases/PD (IR, 95% CI) ²	n/N¹	Cases/PD (IR, 95% CI) ²	n/N¹	Cases/PD (IR, 95% CI) ²	n/N¹	Cases/PD (IR, 95% CI) ²
HIV										
HSV-2										
Syphilis										
NG										
СТ										
UTI										
Pregnancy										

1. Number of women (n) who developed at least one incident infection during the specified time period as a proportion of the women who completed all follow-up visits in that time period (N).

2. Incident rate (IR): Number of incidence cases per person-days of follow-up, with 95% confidence intervals (CI).

Incidence rate ratios (IRRs) with 95% confidence intervals will be calculated comparing each product use group (groups 2-4) to the control group (group 1) using the IR function in STATA. In addition, IRRs with 95% confidence intervals will be calculated comparing each vaginal probiotic group (group 3 and 4) to the metronidazole group (group 2). As before, these IRRs will be calculated for each primary efficacy outcome for the entire follow-up period.

	Group 2 vs 1 IRR (95% CI)	Group 3 vs 1 IRR (95% CI)	Group 4 vs 1 IRR (95% CI)	Group 3 vs 2 IRR (95% CI)	Group 4 vs 2 IRR (95% CI)
HIV					
HSV-2					
Syphilis					
NG					
СТ					
UTI					
Pregnancy					

The number of incident infections will likely be too small to allow for per-protocol analyses and GEE models as described for the primary efficacy outcomes in 6.3 and 6.4.

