4.3 Sample size

This pilot study is descriptive and one of its aims is to inform sample size calculations of a future efficacy trial. Formal sample size calculations were therefore not performed. In the clinical trial, 60 women will be randomised into 4 groups consisting of 15 women each. Based on previous experiences with reproductive health clinical trials in the same study population, we expect to have to screen at least 120 women to enrol 60.

In the qualitative research, the number of FGDs or IDIs held will be governed by data saturation: no new discussions/interviews will be done when they no longer generate new information. The sample sizes listed in this study protocol are estimates based on our previous experiences with qualitative research. For feasibility objective 1, we expect to conduct quantitative face-to-face interviews with at least 30 women attending recruitment sessions who did not pass pre-screening (in addition to the approximately 120 women attending screening visits) and conduct 2 FGDs with women enrolled in

the trial. For feasibility objective 2, we expect to conduct 2 FGDs and 5 IDIs (in addition to quantitative face-to-face interviews with the 60 women enrolled in the trial). For feasibility objective 3, we expect to conduct one FGD with all 12 women in the frequent sampling subgroup. For feasibility objective 5, we expect to conduct 5 IDIs with clinicians and policymakers. The total number of FGDs and IDIs will therefore be approximately 5 FGDs and 10 IDIs.

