1.2 Visit windows and retention definitions

Visit windows for the study visits were as follows:

- Screening + results visits: the entire screening process should not have taken longer than 6 weeks
- Enrolment visit: maximum of 3 days after completion of oral metronidazole treatment
- Day 7: Day 5 Day 9
- Month 1: ± 7 days
- Month 2: ± 7 days
- Month 6: ± 7 days

The following retention definitions were used:

- Early withdrawal: The participant informed a RU staff member that she no longer wants to participate in the study.
- Late visit: The participant did attend a study visit but after the visit window had closed.
- Skipped visit: The participant did not attend a study visit but did return to the study clinic for a subsequent study visit.
- Lost-to-follow-up: RU does not label a participant as lost to follow-up until study close-out. A participant is considered lost to follow-up at study close-out when multiple contact attempts by RU staff failed (as specified in the RU SOP for Retention) and the participant did also not return to the study clinic spontaneously before study close-out.
- Missed visit: All visits that should have taken place according to the study protocol but did not. This includes all study visits after an early withdrawal or after the last study visit made by a participant who is lost to follow-up, as well as all skipped visits.

2. Primary and secondary clinical endpoints

The endpoints of the study discussed in this SAP are:

Primary clinical objectives	Endpoints
1. To determine the safety of the	- Self-reported solicited and unsolicited (serious) adverse events
three biomedical interventions	(AEs) and social harms
compared to the control group.	 Clinician-observed speculum exam findings
2. To determine the preliminary	– BV by Amsel criteria, Nugent score 4-10* (versus 0-3), TV by
efficacy of the three biomedical	culture and symptomatic vaginal candidiasis at any time during
interventions compared to the	the intervention (Day 7, Month 1, Month 2)
control group in reducing BV	– BV by Amsel criteria, Nugent score 4-10* (versus 0-3), TV by
recurrence without increasing	culture, and symptomatic vaginal candidiasis after cessation of
vaginal candidiasis incidence.	the intervention (Month 6)
	* Abnormal Nugent scores will also be analysed as Nugent score
	7-10 versus 0-6.
Secondary clinical objectives	Endpoints

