2. To determine preliminary	- Incidence of the following STIs between screening and Month
efficacy of the three biomedical	6: HIV, HSV-2, syphilis, CT and NG
interventions compared to the	 Incidence of UTI between screening and Month 6
control group in reducing the	
incidence of STIs and UTI.	

3. Participant flow

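### Month 6 HIV and STI cases are counted from a Screening test but time at risk starts at Enrolment, so events and person-days cover different intervals

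*SAP*

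**What the plan says.** On test times, SAP 8.1 states: "Women were tested for HIV and STIs (HSV-2, syphilis, CT, and NG) at the Screening and M6 visits". The schedules of assessments (Protocol 15.2; SAP Table 1) agree. No blood is drawn at Enrolment, and NG/CT PCR there is optional. SAP 8.1 also allows extra tests at Day 7, Month 1 and Month 2 when clinically indicated.

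On what counts as an event, the HIV rule is "therefore, all positive results at M6 will be treated as incident cases", and HSV-2 and syphilis have equivalent rules. For NG the rule is "a positive result for NG PCR at M6 after a negative NG PCR result at Screening (time at risk will start at the Enrolment visit". A separate branch covers women whose NG was treated after randomisation; their clock begins once that treatment is finished. CT has the same wording.

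On the clock, the HIV, HSV-2 and syphilis definitions each end with "Time at risk will start at the Enrolment visit".

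On the interval, the endpoint table in SAP Section 2 gives "Incidence of the following STIs between screening and Month" 6, and Protocol 4.2 says the same. The opening paragraph of SAP 8.1 takes the Enrolment result as baseline where there is one and the Screening result otherwise.

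**The concern.** A woman who is negative at Screening and positive at Month 6 may have been infected at any time between the two tests. SAP 8.1 counts her as a case but starts her person-days at Enrolment. The numerator therefore runs from Screening to Month 6 and the denominator only from Enrolment to Month 6. The Enrolment start suits UTI and pregnancy, which are tested at that visit. For the five infections it is applied without a scheduled test at that visit.

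The gap is part of the design, because every randomised woman completes seven days of metronidazole between Screening and Enrolment. At stake are the absolute rates that this pilot will report and, to a lesser degree, the comparisons between groups, since some counted infections would precede randomisation and could not have been affected by any intervention.

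**Working it through.** The documents give no rate, event count or person-days for these endpoints (SAP 3.1 lists person-days as still to be determined), so there is no planned figure to reproduce. The check asks how large the mismatch can be.

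**Inputs**
- T, days from Enrolment to Month 6: taken as 182 (assumption; 173 to 187 also tried).
- g, days from Screening to Enrolment, built from the documents:
  - 7 to 10 if metronidazole starts at Screening (7 days of treatment, then an Enrolment window of 0 to 3 days; Protocol 6.2, SAP 1.2).
  - 14 to 24 if treatment waits for the results visit 1 to 2 weeks later (7 + 7 + 0 = 14; 14 + 7 + 3 = 24).
  - 42 at the limit in SAP 1.2: "the entire screening process should not have taken longer than 6 weeks".
  - 52 if treatment and the window follow a full six weeks (42 + 7 + 3).
- A constant infection rate from Screening to Month 6 (assumption).

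**Rate inflation for a rare endpoint.** Events arise over g + T days and person-time covers T days, so the factor is (T + g)/T. The share of counted events that precede randomisation is g/(T + g).

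| g (days) | (T + g)/T | Pre-randomisation share |
|---|---|---|
| 7 | 189/182 = 1.04 | 4% |
| 10 | 192/182 = 1.05 | 5% |
| 14 | 196/182 = 1.08 | 7% |
| 24 | 206/182 = 1.13 | 12% |
| 42 | 224/182 = 1.23 | 19% |
| 52 | 234/182 = 1.29 | 22% |

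With T between 173 and 187 the factor runs from 1.04 to 1.30 over the same gaps.

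**Effect of the missing end rule.** Suppose every case is counted up to the Month 6 test and infections persist until then. Cases then add days after infection, which offsets the inflation. With daily rate λ = −ln(1 − risk)/T, where risk is the risk over T days, the factor becomes [1 − exp(−λ(T + g))]/(λT). At 20% risk and g = 24, λ = 0.2231/182 = 0.001226, and the factor is 0.2232/0.2231 = 1.00. Other values:

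| Six-month risk | g = 10 | g = 24 | g = 52 |
|---|---|---|---|
| 2% | 1.04 | 1.12 | 1.27 |
| 5% | 1.03 | 1.10 | 1.24 |
| 20% | 0.94 | 1.00 | 1.12 |
| 30% | 0.88 | 0.93 | 1.03 |

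If each case is instead credited with half of the Enrolment-to-Month 6 interval, the inflation stays close to the first table (g = 24: 1.13 at 2% risk, 1.12 at 30%).

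**Effect on the incidence rate ratio.** The gap adds the same pre-randomisation risk to every group in expectation. If the true ratio after randomisation is R, the observed ratio is (g + R·T)/(g + T). For R = 0.50:
- g = 10: (10 + 91)/192 = 0.53
- g = 24: (24 + 91)/206 = 0.56
- g = 52: (52 + 91)/234 = 0.61

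The pull comes from which events are counted. A new start date for person-days scales all groups alike and leaves it in place.

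**The case against.** The best case for leaving this alone is practical. SAP 8.1 itself says the sample is too small to test these hypotheses adequately and expects too few infections for per-protocol or GEE analyses. As an illustration, with an assumed 5 events the exact 95% Poisson interval for the count is 1.6 to 11.7, about sevenfold, so a shift of 4–13% is small beside it. This stands as an argument about weight. It does not justify a rate whose two parts cover different intervals.

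Some women are unaffected. Those treated for CT or NG during follow-up already start at treatment completion. An Enrolment swab may have been tested, and SAP 8.1 would then use it as baseline. Women who were syphilis-positive at Screening and treated before randomisation have no negative Screening test to start from, so moving every clock to Screening would count infected time as time at risk.

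Four stronger readings are tempting, and the documents do not support them:
- A reader might infer that all five rates are too high. That is secure only for rare endpoints such as HIV. For CT and NG, where 26 of 68 randomised women were already infected (8 + 7 + 4 + 7; SAP 6.3), the sign depends on the unstated end rule.
- A reader might infer that women infected before randomisation contribute no person-time. They still contribute days after Enrolment; only the Screening-to-Enrolment interval is lost.
- A reader might infer that the error cancels in the rate ratios. It does so only if the true ratio is 1.
- A reader might infer that the efficacy trial will be too small as a result. Protocol 4.3 says of the pilot that "one of its aims is to inform sample size calculations of a future efficacy trial", but does not name STI incidence as the planning input.

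**Conclusion.** The mismatch is real and stands in the wording of SAP 8.1, which also disagrees with the interval in SAP Section 2 and Protocol 4.2. It applies to HIV and HSV-2, to syphilis in women negative at Screening, and to CT and NG in women negative at Screening with no Enrolment result.

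For rare endpoints the overstatement is about 4–5% or 8–13% on the usual routes through screening. It reaches 23–29% only if the six-week limit is used in full. These sizes rest on 182 days of follow-up, a constant infection rate and gaps derived from the visit rules, because the documents report no observed gaps. For common endpoints the direction cannot be settled until the SAP says when a case stops contributing person-days. Rate ratios are pulled modestly toward 1. This is a defect in the definition of secondary endpoints, worth correcting because correction is cheap; it does not touch the primary analyses.

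**What to change.** Rewrite the time-at-risk rules in SAP 8.1 for each endpoint:
- **HIV, HSV-2, CT, NG, and syphilis in women negative at Screening:** start at the last negative test. For CT/NG this is Enrolment if an Enrolment result exists, and otherwise Screening; for the others it is Screening.
- **Women treated for syphilis before randomisation, or for CT/NG during follow-up:** start at treatment completion (already the rule for CT/NG).
- **Cases:** end person-time at a stated event date, for example the midpoint between the last negative and first positive test. For women who start at treatment completion, use the midpoint from that date.
- **UTI:** keep the Enrolment start. **Pregnancy:** state it, since SAP 8.1 gives no start.
- **SAP Section 2:** align the interval with these rules endpoint by endpoint. Its UTI line also runs from screening.

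Report the observed Screening-to-Enrolment gaps, and note beside the rate ratios that some counted infections may precede randomisation. Testing stored Enrolment endocervical swabs (Protocol 6.4) would give a true CT/NG baseline and is the only step here that reduces the pull toward 1, at laboratory cost.

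The rest costs a change of SAP wording and the use of visit, test and treatment dates that the trial should already hold. The downside is that the stated rates become slightly lower.

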Participants used their study products (if applicable) for 2 months, and returned for study visits after seven days (D7), one month (M1) and two months (M2; cessation of product use), and then again at six months (M6; 4 months after cessation of product use). At these follow-up visits, participants underwent a face-to-face interview, speculum examination and a variety of laboratory tests (BV by Amsel criteria and Nugent scoring, TV by wet mount and InPouch culture, candidiasis by wet mount, and additional testing if clinically indicated). At the M6 visit, HIV, STI, pregnancy and UTI tests were repeated. Please refer to Table 1 below for a full schedule of assessments by study visit.

Figure 1: Flow diagram of study visits and numbers of women seen at each visit

Table 1: Schedule of assessments

Procedures in clinic during visits	Screening/results	Enrolment	D7, M1, M2	M6
Informed consent	Х	Х		
Contact information	X	Х	X	Х
Assign PIN	X			
Eligibility checklist	X	Х		
Randomisation: initiate interventions		Х		
Cease interventions			X (M2)	
Face-to-face interview, quantitative	X	Х	X	Х
Discussion/interview, qualitative				
Assess AEs and social harms		Х	X	Х
HIV pre- and post-test counselling	X			Х
HIV/STI/BV risk reduction counselling	X	Х	Х	Х
Blood collection (10 ml)	X			Х
Urine collection	X	X		Х
Rapid HIV testing (whole blood) ¹	X			Х
Rapid pregnancy testing (hCG urine)	X	Х	[X]	Х
Rapid UTI testing (urinalysis dipstick)	X	Х	[X]	Х
Speculum exam: visual inspection	X ²	Х	X	Х
Speculum exam: vaginal pH + wet mount (TV,	X ^{2,3}	X ³	X ³	X ³
candida, BV by Amsel ²)				
Speculum exam: vaginal swabs	X	X	X	Х
Speculum exam: endocervical swabs	X ²	Х	[X]	Х
Speculum exam: CVL	X ²	X	X	Х
Provide results and treatment if appl ¹	X	X	X	Х
Laboratory procedures after visits				
Blood: syphilis and HSV-2 serology	Х			X ⁴
Endocervical swab: NG/CT PCR	Х	[X] ⁵	[X] ⁵	Х
Vaginal swabs: TV InPouch culture	Х	X	X	Х
Vaginal swabs: Nugent scoring	Х	Х	Х	Х
Vaginal swabs: store for VMB MiSeq	X	Х	Х	Х
Laboratory procedures if funding permits:	•			
Vaginal swabs: store for additional VMB	X	х	Х	х
assessments (e.g. qPCR, biofilm)				
CVL: store for additional VMB assessments	X	x	X	Х
Vaginal smears: store for biofilm assessments	X	х	X	x

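### Incident syphilis (SAP 8.1) can include a persisting positive in a woman treated after Screening, because no negative result is required before Month 6

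*SAP*

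**What the plan says.** The endpoint in SAP 8.1 is "Syphilis: a positive result for the syphilis serology algorithm at M6". Women positive at Screening are not removed from the risk set. The SAP says that they "were adequately treated prior to randomisation; therefore, all positive cases at M6 will be treated as incident cases", and time at risk starts at Enrolment.

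On testing times, the same section states: "Women were tested for HIV and STIs (HSV-2, syphilis, CT, and NG) at the Screening and M6 visits". It adds that "additional testing may have been done at the D7, M1 and M2 visits when clinically indicated", but the syphilis definition makes no use of such tests. In SAP Table 1 the row "Blood: syphilis and HSV-2 serology" is marked at Screening/results and at M6 and is blank at Enrolment and at D7, M1 and M2. The protocol schedule (15.2) agrees.

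The general baseline rule in 8.1 is "using endpoint data from the Enrolment visit if available and otherwise from the Screening visit". No syphilis test is scheduled at Enrolment, so for syphilis the baseline is the Screening result.

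The restriction on retesting at M6 covers one infection only: "Only those participants who tested negative for HSV-2 at Screening were retested at M6". Women positive for syphilis at Screening are therefore retested at M6.

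**The concern.** Having been treated is not the same as having tested negative. A woman positive at Screening and again at M6 may carry the first infection's serological response or may have a new infection. Without a result in between, or a rule on change in titre, the data cannot separate the two, and the SAP settles the matter by counting all such cases as new.

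The SAP takes more care elsewhere. For the primary outcomes, section 6.1 plans a case-by-case assessment to separate incident from persisting infections, including whether treatment was properly dispensed and taken. Section 8.1 has no such step for syphilis.

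At stake are the syphilis incidence rate in each arm and the five between-group rate ratios tabulated in 8.1. Few events are likely, so a single misclassified case can dominate an arm's rate.

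**Working it through.** The documents give no syphilis count, power or effect size, so there is no planned figure to reproduce. The check has two parts.

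**1. Can a persisting positive reach the numerator?**

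- *Entry.* Protocol 6.3 treats a syphilis-positive woman and asks her back for a repeat wet mount. If that shows BV or TV, she takes metronidazole and proceeds to enrolment. No repeat serology is listed.
- *Between treatment and M6.* No syphilis test is scheduled. A clinically indicated test (SAP 8.1) or a repeated screening (protocol 6.3) could exist, but neither is required.
- *At M6.* She is retested, because the restriction in SAP Table 1, footnote 4, concerns HSV-2 only.
- *Positivity.* The footnotes to SAP table 4.1 define the algorithm as haemagglutination with RPR confirmation. There is no titre criterion, so a woman still RPR-positive at M6 meets the definition.

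The rule therefore admits a persisting positive. Whether any such woman was randomised is a separate question. The text of table 4.1 is broken, but syphilis appears to be marked 0* for randomised women, with a footnote that such conditions cannot be present in them. Table 4.2 omits syphilis. Against this, SAP 8.1 speaks of participants positive at Screening who were treated before randomisation, and protocol 6.3 provides a route for them.

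**2. How much would one case matter?**

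From the SAP: 17 women per arm, 68 in total, 64 seen at M6. Assumption: 180 days at risk per woman.

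Rate = k/T, with exact Poisson limits (for k = 0 the upper limit is −ln(0.025)/T = 3.689/T).

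- Arm person-days: 17 × 180 = 3,060.
- One case: 1/3,060 = 0.33 per 1,000 person-days (95% CI 0.01 to 1.82), about 11.9 per 100 person-years. With 173 to 187 days per woman (the M6 window) the rate is 0.34 to 0.31.
- No case: 0, upper limit 3.689/3,060 = 1.21 per 1,000. If the woman's own 180 days are also removed, T = 2,880 and the upper limit is 3.689/2,880 = 1.28.
- Whole study: 1/(64 × 180) = 1/11,520 = 0.09 per 1,000.

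Rate ratio with equal person-days and a and b cases: given a + b, a is binomial with p = IRR/(1 + IRR). Exact limits for p are converted by p/(1 − p).

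| Cases (a, b) | IRR | 95% CI |
|---|---|---|
| 1, 1 (true cases only) | 1.0 | 0.01 to 78.5 |
| 2, 1 (one carried over in the product arm) | 2.0 | 0.10 to 118 |
| 1, 2 (one carried over in the control arm) | 0.5 | 0.01 to 9.6 |

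Expected number of carried-over cases = 68 × s × r, where s is the share of randomised women positive at Screening and r the share of those still positive at M6. P(at least one) = 1 − (1 − s·r)^68. The documents give neither share, so the values below are assumptions.

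| s | r | Expected | P(at least one) |
|---|---|---|---|
| 2% | 10% | 0.14 | 0.13 |
| 5% | 30% | 1.02 | 0.64 |
| 10% | 50% | 3.4 | 0.97 |

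If s = 0, as table 4.1 may imply, all of these are zero.

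**The case against.** The strongest reply is that the SAP consistently treats a cured woman as again at risk. TV and UTI are counted as incident after adequate treatment. NG is counted not only as "a positive result for NG PCR at M6 after a negative NG PCR result at Screening" but also after successful treatment, and CT likewise, with no test of cure named. This stands. A reader might infer that syphilis is handled more loosely than NG and CT, but the documents do not support that contrast and the point does not rest on it.

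HSV-2 is also an imperfect model. The protocol lists syphilis among the curable infections, and a treated woman in this high-risk population can be reinfected. A rule that removed every Screening-positive woman outright would lose true reinfections, including any with a documented negative in between. This too stands, and it is why the fix accepts such a negative and keeps the remaining women visible.

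Three further limits hold. RPR confirmation means that haemagglutination positivity alone does not count. Unscheduled tests or repeated screening may have produced a negative result for some women. The SAP itself says the study is too small to test these hypotheses, and the interval for the ratio is uninformative with or without a misclassified case.

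None of this removes the gap. For a treated woman without an interim negative who is RPR-positive at M6, the classification as incident rests on assumption alone.

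**Conclusion.** The point holds as a flaw in an endpoint definition: SAP 8.1 can count a persisting positive as a new infection. One such case would add about 0.33 per 1,000 person-days to an arm (assuming 180 days per woman) and could double or halve a rate ratio built on one true case per arm.

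A reader might go further and infer that persisting positives did enter the numerator, or that the syphilis rate ratios are biased. The documents do not show this. They do not say how many randomised women were positive at Screening, and the apparent 0* in table 4.1 would make it none. Nor does that marking prove the group empty: the table is broken, the mark may reflect status after treatment, and SAP 8.1 itself refers to such participants. The passages must be reconciled.

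The primary efficacy and safety analyses are untouched. This is a cheap improvement to a secondary endpoint that the SAP already calls underpowered.

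**What to change.** In SAP 8.1:

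1. Count syphilis at M6 as incident only in women negative at Screening, or with a documented negative result after treatment and before M6.
2. State how many randomised women, by group, were positive at Screening, and reconcile table 4.1 with SAP 8.1 and protocol 6.3.
3. Keep women positive at Screening without a documented later negative out of the main rate, the rate ratios and their person-time. List separately those positive again at M6.
4. Add a sensitivity analysis that counts the listed women as incident.

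Cost: a sentence or two and one short listing, with no new data. Each woman left out removes about 180/3,060 = 5.9% of an arm's person-days (same 180-day assumption). The downside is that a true reinfection in a treated woman with no interim negative is listed but does not count in the main rate; the sensitivity analysis shows its effect. If no randomised woman was positive at Screening, the change reduces to one statement saying so.
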